Section contains only negative-fluorescence	Collect 1 fluorescence-negative biopsy as far away (at least ≥ 1 cm specimen size permitting) from the border of palpable mass as is possible.	Collect 1 fluorescence-negative biopsy as far away (at least ≥ 1 cm specimen size permitting) from suspected-carcinoma in an area suspected to be normal tissue.

12.4.4.2. Specimen Grossing

All specimens (excluding biopsies taken from the *primary specimen*) will be individually weighed prior to fixation in formalin, and the mass (mg) will be recorded on the Pathology Data Collection Tool.

Specimen grossing and fixation will be performed as per SoC, including inking of all surfaces of the *primary specimen* and both the inside and outside surface of all *cavity shave specimens*. To adjudicate the *orientation-level* endpoints, the inside and outside surfaces of all *cavity shave specimens* must be inked with different colors (visually obvious) of ink. The *primary specimen* and any *cavity shave specimens* will be submerged in formalin within the site-mandated time post-resection (i.e. ischemic time).

12.4.5. Post-Operative Procedures

Prior to discharge, participants will be evaluated for any adverse events. At the 2-week follow-up visit the *surgeon* will assess the participant for any adverse events including any self-reported signs/symptoms. All AEs will be reported in the participants medical record and in the eCRF. The participant will be administered the post-operative Breast-Q survey.

The participant will be provided sunscreen to apply at time of discharge and for a minimum of 48 hours following administration of the investigational drug when exposed to sunlight. Application of sunscreen at time of discharge will be confirmed and recorded in the case report form. The participant may be administered additional medications (e.g. antiemetics) to mitigate the side effects of PD G 506 A, as medically required.

SBI-CIP Rev: 20-002 v1.8	A prospective multi-center clinical study evaluating the use of PD G 506 A and the Eagle V1.2 Imaging System for the visualization of carcinoma during breast conserving surgery	Page: 74 of 157
--	--	-----------------

Participants will receive postoperative treatment (e.g. radiation, chemotherapy, re-operation) as per standard of care. All postoperative treatment that is initiated within the study period (until the Week 2 visit) will be recorded in the eCRF.

12.5. Day 2 Follow-up (24 hours +24 hours post-surgery)

Between 24 – 48 hours after the surgery the participant will be contacted via telephone and asked about their adherence to the sun protection instructions, any self-reported adverse events and concomitant medications.

12.6. Post-operative Pathology Procedures (no visit)

12.6.1. Specimen Blocking and Assessment

The *primary specimen* will be blocked according to standard procedures. All *cavity shave specimen(s)* will be blocked in total.

Cavity shave specimens must be oriented such that histological sections can be made perpendicularly to the *inked inside* and *outside surfaces*. Biopsies must be oriented such that histological sections can be made perpendicularly to the *inked surface* (i.e., imaged surface).

Primary Specimen:

The pathologist will evaluate the *primary specimen* as per SoC and record the following for each anatomical surface (i.e., S, M, P, L, I, A) on the Pathology Data Collection Tool:

- i. Presence or absence of carcinoma at each *inked surface*,
- ii. Presence or absence of carcinoma below each inked surface.
- iii. Presence or absence of non-malignant abnormal cells (e.g. hyperplastic, dysplastic) at or below each inked surface

If carcinoma is present, record the following additional information on the Pathology Data Collection Tool:

- i. Type(s) of carcinoma (e.g. IDC, ILC, DCIS, if other specify)
- ii. Shortest distance from the *inked surface* to carcinoma

If non-malignant abnormal cells are present, record the following additional information: Type(s) of abnormal cells (e.g. hyperplastic, dysplastic, etc.)

Cavity Shave Specimens:

The pathologist will evaluate all *cavity shave specimen(s)* and record the following on the Pathology Data Collection Tool (note: *cavity shave specimen(s)* must be histologically assessed in total):

i. Presence or absence of carcinoma at or below the *inked outside surface* of all *cavity shave specimens*

- ii. Presence or absence of carcinoma at or below the *inked inside surface* of all *cavity shave specimens*
- iii. Presence/absence of non-malignant abnormal cells (e.g. hyperplastic, dysplastic) at or below the *inked inside surface* of all *cavity shave specimens*

If carcinoma is present, record the following additional information on the Pathology Data Collection Tool:

- i. Type(s) of carcinoma (e.g. IDC, ILC, DCIS, if other specify)
- ii. Shortest distance from each *inked surface* (i.e., inside and outside surfaces) to carcinoma

If non-malignant abnormal cells are present, record the following additional information:

i. Type(s) of abnormal cells (e.g. hyperplastic, dysplastic, etc.)

Tissue Biopsies:

The pathologist will evaluate all specimen biopsies and record the following on the Pathology Data Collection Tool (note: *biopsies* must be histologically assessed in total):

- i. Presence/absence of carcinoma anywhere in a given biopsy
- ii. Presence/absence of non-malignant abnormal cells (e.g. hyperplastic, dysplastic) anywhere in a given biopsy

If carcinoma is present, record the following additional information on the Pathology Data Collection Tool:

- i. Type(s) of carcinoma (e.g. IDC, ILC, DCIS, if other specify)
- ii. Shortest distance from the inked surface to carcinoma

If non-malignant abnormal cells are present, record the following additional information:

i. Type(s) of abnormal cells (e.g. hyperplastic, dysplastic, etc.)

Lastly, the pathologist will report the final margin status in the participants medical record as well as the Pathology Data Collection Tool.

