Exploratory Objective	Parameter Description	Parameter Formula		Abbreviated Description
21. To characterize the diagnostic performance of imaging of PD G 506 A to identify malignant breast tissue (Arm 2 only).	Percentage of FL guided shaves that had no cancer on histopathology.	P(E.21) = # FL-driven shave specimens with no carcinoma anywhere # of FL-driven shave specimens	x 100%	Carcinoma negative FL-driven shave specimens.
22. To investigate the depth of carcinoma tissue that can be visualized by PD G 506 A using the Eagle V1.2 Imaging System.	Depth of tumor identified by FL imaging relative to the inked surface, reported by tumor type (invasive carcinoma and DCIS), using descriptive statistics (e.g., mean, median, and range).			Depth of FL visualization.
23. To investigate the depth of carcinoma tissue that can be visualized by PD G 506 A using the Eagle V1.2 Imaging System.	Percentage of specimens where invasive carcinoma was located only below the inked surface (i.e., inked surface cancer free) for the surfaces imaged ex vivo (primary specimen or shave specimens) where FL detected invasive carcinoma.	P(E.23)= #FL-positive orientations-ex vivo where invasive carcinoma was located only below the inked surface (i.e., inked surface cancer free) #FL-positive orientations ex vivo with invasive carcinoma	x 100%	Fluorescence visualization of invasive carcinoma below the imaged surface.
24. To investigate the depth of carcinoma tissue that can be visualized by PD G 506 A using the Eagle V1.2 Imaging System.	Percentage of specimens where DCIS was only located deeper than 2 mm below the inked surface (i.e., DCIS not within 2 mm of the inked surface) for the surfaces imaged ex vivo (primary specimen or shaves) where FL detected DCIS.	P(E.24) = #FL-positive DCIS orientations- ex vivo where DCIS was only located deeper than 2 mm below the inked surface (i.e., DCIS not within 2 mm of the inked surface) #FL-positive orientations-ex vivo with DCIS	x 100%	Fluorescence visualization of DCIS > 2 mm below the imaged surface.

carcinoma during breast conserving surgery
--

Exploratory Objective	Parameter Description	Parameter Formula		Abbreviated Description

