8.3. Minimizing Bias

The following precautions are in place to minimize bias in data collection:

- No personnel involved with the surgical procedure (i.e., *surgeon*, *surgeon's assistant*) will be aware of the participant's randomized treatment assignment nor be present when the participant is provided with the study drug to ingest.
 - o Blinded research personnel will be instructed not to solicit any information from the participant regarding the taste and/or smell of the investigational drug.
- The participant will be blinded to whether they have been randomized to Arm 1 or Arm 2 for the duration of the study.
- The *surgeon* will be blinded to whether a participant has been randomized to Arm 1 or Arm 2 until the time at which the *surgeon* declares the SoC lumpectomy is complete.
- The individual (e.g. pathologist's assistant, pathologist) processing the surgical specimen(s) will be blind to the manner (e.g. SoC vs. *FGR*) by which samples are obtained and the FL status of the samples. This individual will also be blind to the fluorescence

SBI-CIP 20-002 Rev: v1.8 A prospective multi-center clinical study evaluating the use of PD G 506 A and the Eagle V1.2 Imaging System for the visualization of carcinoma during breast conserving surgery	Page: 47 of 157
---	-----------------

- imaging data collected of the bisected/serially sectioned primary specimen during the perioperative procedures.
- The pathologist performing the histopathological evaluation will be blind to the manner (e.g. SoC vs. *FGR*) by which the samples are obtained and the FL status of the samples.
- To ensure FL-imaging does not influence **SoC margin assessment**, intraoperative data collection tools will document the completion of SoC prior to the **surgeon** being given access to any previously acquired FL imaging data and performing additional FL imaging.

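### Section 12.6.1 asks for one distance to carcinoma per inked surface, not one per tumour type, so E.22 and part of E.24 cannot be derived where invasive carcinoma and DCIS share a surface

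*Combined protocol and SAP*

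**What the plan says.** For the primary specimen, Section 12.6.1 lists presence of carcinoma at the ink and below it for each anatomical surface, then "Type(s) of carcinoma (e.g. IDC, ILC, DCIS, if other specify" and "Shortest distance from the *inked surface* to carcinoma". For cavity shaves the presence item merges the two positions, "Presence or absence of carcinoma at or below the *inked outside surface* of all *cavity shave specimens" (with a matching item for the inside surface), followed by the type list and "Shortest distance from each *inked surface* (i.e., inside and outside surfaces) to carcinoma". Appendix 2 repeats these items. In neither place is a distance tied to a type.

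Section 7.3 uses type-specific depth. E.22 is depth "relative to the inked surface, reported by tumor type (invasive carcinoma and DCIS), using descriptive statistics". E.23 concerns invasive carcinoma lying only below ink and glosses this as an inked surface free of cancer. E.24 applies a cut to DCIS alone: "i.e., DCIS not within 2 mm of the inked surface". Mixed disease is eligible (Section 9.2) and falls in a randomisation stratum (Section 8.1).

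On blinding, Section 8.3 states: "The pathologist performing the histopathological evaluation will be blind to the manner (e.g. SoC vs. *FGR*) by which the samples are obtained". Section 12.4.3 keeps the reason for each shave off its label. At the end of Section 12.6.1, "the pathologist will report the final margin status in the participants medical record" and on the Pathology Data Collection Tool. Section 12.7 names the surgical pathology report as a second source of endpoint data, and Section 12.6.2 requires tissue blocks to be kept.

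**The concern.** If a surface is listed with both IDC and DCIS and one distance of 1 mm, the record does not show which type lies at 1 mm or how far away the other is. Two exploratory endpoints need exactly that information.

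The same gap could reach further. Section 5.1 requires margin status both after SoC and after FGR. When a fluorescence-driven shave has been taken, the last SoC surface is no longer the final margin, and the pathologist does not know which surface it was. After-SoC status then has to be assembled from the surface-level items. Every conversion in P(1.1) involves such a shave, because a margin cannot turn from positive to negative without more tissue being removed. After-SoC status also sets the denominator of P(2.1), and the end-of-SoC surface histopathology (Section 15.4.4.1) sets the patient classification behind P(2.2) and P(2.3).

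**Working it through.** **Step 1: what one distance determines.** Take a surface carrying both types. Let a be the distance to invasive carcinoma and b the distance to DCIS. The recorded value is d = min(a, b), with the nearer type not named. Both a and b are therefore at least d, and one of them equals d.

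| Quantity | d = 0 | 0 < d < 2 mm | d = 2 mm | d > 2 mm |
|---|---|---|---|---|
| E.22, depth of each type | not derivable | not derivable | not derivable | not derivable |
| E.23, as glossed (surface cancer free) | no | yes | yes | yes |
| E.24, DCIS only deeper than 2 mm | not derivable | not derivable | not derivable | yes |
| Margin, assumed rule A | positive | ambiguous | negative | negative |
| Margin, assumed rule B | positive | negative | negative | negative |

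- E.22: d belongs to an unnamed type and the other depth is known only to be at least d. At least one depth is missing at every d.
- E.24: if d > 2 mm then b > 2 mm and the answer is yes. If d ≤ 2 mm, either DCIS is at d (answer no) or invasive carcinoma is at d and DCIS may lie anywhere from d outwards (answer unknown).
- E.23: any d > 0 shows the ink is free of cancer; d = 0 shows it is not.
- Rule A (assumption): positive if invasive carcinoma is on ink or DCIS is closer than 2 mm. At d = 1 mm, a = 1 and b = 3 is negative, while a = 3 and b = 1 is positive, and both leave the same record.
- Rule B (assumption): in mixed disease, positive only if carcinoma is on ink. One distance then settles every surface.

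Surfaces with a single tumour type are unaffected throughout.

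**Step 2: which patients need a derived after-SoC status.** With no fluorescence-driven shave, Section 5.1 makes the margins after FGR the same as those after SoC, so the status the pathologist reports serves directly. Derivation from surface items is needed only when such shaves were taken.

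**Step 3: the plan's own sample size.** Inputs from Section 15.2: null 1%, expected 3%, two-sided 0.05, power 90%, one-sample Z test.

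n = [(1.960 × √(0.01 × 0.99) + 1.2816 × √(0.03 × 0.97)) / 0.02]² = 427.7, rounded up to 428. Then 428 × 7/6 = 499.3, planned as 500. The stated figures reproduce, and this point does not change them.

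**Step 4: sensitivity of P(1.1), not a forecast.** Expected conversions are 0.03 × 428 = 12.84. The Wilson lower bound is 0.95% with 8 conversions and 1.11% with 9, so 9 are needed. Exact binomial power at 3% is 89.6%.

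| Expected converters lost | Rate | Power |
|---|---|---|
| 1 | 11.84/428 = 2.77% | 83.8% |
| 2 | 10.84/428 = 2.53% | 75.7% |
| 3 | 9.84/428 = 2.30% | 65.1% |

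The documents do not say how many patients, if any, would be misclassified. Errors could also run the other way and add false conversions.

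**The case against.** The endpoints certainly affected, E.22 and E.24, are exploratory, and E.22 is purely descriptive. The Pathology Data Collection Tool is not among the documents and may already hold one row per type. The surgical pathology report is a stated second source, and retained blocks allow re-reading. Shaves are numbered in order of removal, so surface results can be mapped to SoC or FGR without unblinding the pathologist. All of this stands, and it limits the point to what the protocol's listed items can support. It does not close the gap: nothing says the clinical report gives distances by type, and no re-read is planned.

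Three stronger readings are tempting, and the documents do not support them.

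- A reader might infer that E.23 fails too. Its own gloss makes it derivable from one distance.
- A reader might infer that after-SoC margin status cannot be worked out in mixed disease. That depends on the Section 5.1 rule. The cuts in E.23 and E.24 describe how deep fluorescence is seen and cannot stand in for it. Even under rule A, only the band between 0 and 2 mm on mixed surfaces is in doubt.
- A reader might assume a share of patients with mixed disease and turn it into a count of misclassified converters. No such step is available. Both types would have to lie on the same surface, with a distance inside the band, on a surface that alone decides the patient's status, in a patient with a fluorescence-driven shave, and with the pathology report not resolving it.

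**Conclusion.** The point holds in limited form. Data collected as Section 12.6.1 and Appendix 2 are written cannot give E.22 on surfaces carrying both types, nor E.24 on those surfaces when the recorded distance is 2 mm or less. E.23 and the sample size are untouched.

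The reach into P(1.1), P(2.1), P(2.2) and P(2.3) is conditional on the margin rule setting a 2 mm limit for DCIS in mixed disease. It is then confined to mixed surfaces between 0 and 2 mm in patients with fluorescence-driven shaves. The amendment summary in Section 2 bases the definition on the 2014 and 2016 guidelines, whose titles in the reference list show one for invasive cancer and one for DCIS. That makes the question reasonable but does not answer it for mixed disease. The count of affected patients is unknown. The power figures show only that, with 9 conversions needed and about 13 expected, even a few errors would matter.

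This is a should-fix: the certain loss is exploratory, the possible loss touches the primary endpoint, and neither can be recovered later without going back to the pathologist or the slides.

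**What to change.** In Section 12.6.1 and Appendix 2, and in the Pathology Data Collection Tool if it does not already do so, require two items at every inked surface, each recorded separately for invasive carcinoma and for DCIS: presence at ink, and shortest distance. For shaves this also separates carcinoma on ink from carcinoma below it, which the present presence item merges. State in the SAP one programmed rule that derives surface status and after-SoC margin status from these fields, including how mixed disease is classified.

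For patients already assessed, re-query only specimens listed with both types. The cost is one extra distance field on mixed surfaces, read from the same slides, plus those limited queries. If the Tool already records distance by type, a clarifying sentence in the two places is enough.

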12.6.2. Specimen Handling, Storage and Future Research

All specimens collected as part of this study will be prepared, handled and stored according to the site's policies and procedures. All tissue blocks will be stored on site and may not be destroyed or discarded prior to the completion of the study and notification by the sponsor that samples are no longer required to be stored. All samples must be logged and tracked over the course of the study and stored in a secure location accessible to research team members delegated responsibility for handling and storing specimens.

During the study and/or at the end of the study, the Sponsor may request specimens collected as part of this study, including unstained histological sections from paraffin embedded tissue blocks and/or tissue blocks (if permitted by the site) in order to answer future research questions. Tissue specimens provided for use in future research will be coded, de-identified and linked to the data

SBI-CIP 20-002 Rev: v1.8 A prospective multi-center clinical study evaluating the use of PD G 506 A and the Eagle V1.2 Imaging System for the visualization of carcinoma during breast conserving surgery	Page: 76 of 157
---	-----------------

collected as part of this clinical study, including for example: patient demographics, disease characteristics, surgical pathology data, the type of specimen (e.g. SoC-guided vs. FL-guided), and the FL-status and histopathological-status of the tissue block and/or surface from which the tissue block was taken. Tissue specimens sent to the Sponsor may be stored indefinitely and may be used to answer future research questions that are either related or unrelated to the clinical study protocol SBI-CIP 20-002. Tissue specimens may be sent to external laboratories for processing (e.g. histological staining) and evaluation (e.g. analysis of stained histological sections). Tissue specimens will not be used for any genetic research. If future analyses of specimens leads to findings that are relevant to a patient's ongoing health, the patient's surgeon will be informed and findings will be shared with the patient. Specimens provided to the Sponsor may also be shared with 3rd parties for the purposes of answering future research questions unrelated to the current study. Specimens shared with 3rd parties will be coded, de-identified and linked to patient demographics, disease characteristics, surgical pathology data. Specimens shared with 3rd parties will not be linked to any personally identifiable patient information.

12.7. Week 2 Visit (Day 10 – 14)

Clinical usefulness and diagnostic performance endpoint data will be collected at the participant's post-operative surgical follow-up visit.

At this visit, the participant will complete the post-operative Breast Conserving Therapy Module of the Breast-Q survey. To minimize the potential impact of timing of administration of the Breast-Q survey post-op questionnaire, all patients will complete the 2-week post-op questionnaire before they have met with their *surgeon* to discuss their surgical pathology report.

The participant's surgical pathology report will be available at this time. Endpoint data will be retrieved from the participant's surgical pathology report and the study-specific Pathology Data Collection Tool. Additional data related to the final pathological tumor staging, pathological features/characteristics and nodal involvement will be retrieved from the participant's surgical pathology report and recorded in the eCRF.

The *surgeon* will question the patient about any patient-reported Aes and use of concomitant medications as well as assess and record any ongoing adverse events in the participant's medical record and eCRF.

Blood work (CBC, AST, ALT, TBL, creatinine) will be performed at this visit. If liver enzymes are elevated from baseline (and deemed clinically significant according to the **Table 12.2** below), the patient will be followed until such time that liver enzyme levels return to baseline. Physical examination must include assessment of any phototoxicity reactions and any observed phototoxicity reactions will be followed until resolution.

Table 12.2: Criteria for clinical significant liver enzyme elevation

	SBI-CIP 20-002	Rev: v1.8	A prospective multi-center clinical study evaluating the use of PD G 506 A and the Eagle V1.2 Imaging System for the visualization of carcinoma during breast conserving surgery	Page: 77 of 157
--	-----------------------	--------------	--	-----------------

Criteria	CTCAE v5.0 Grade 2 (moderate) as criterium to judge if elevation of liver enzymes should be deemed clinically significant
Bilirubin: above upper limit of normal	Bilirubin:
	> 1.5 – 3.0x institutional* ULN if baseline normal
	> 1.5 – 3.0x baseline if baseline abnormal
AST: > 2.5x institutional ULN	AST:
	> 3.0 – 5.0x institutional* ULN if baseline normal
	> 3.0 – 5.0x baseline if baseline abnormal
ALT: > 2.5x institutional ULN	ALT:
	> 3.0 – 5.0x institutional* ULN if baseline normal
	> 3.0 – 5.0x baseline if baseline abnormal
AP: n/a	AP:
	> 2.5 – 5.0x institutional* ULN if baseline normal
	> 2.5 – 5.0x baseline if baseline abnormal

^{*&}quot;institutional" is included in the study protocol definition, not part of the original CTCAE definition

12.8. 3-Month Follow-up (Day 80 - 90)

The participant will be required to complete the post-operative Breast Conserving Therapy Module of the Breast-Q survey within 80 to 90 days post-surgical procedure. If the participant is scheduled to receive radiation therapy prior to 80 days post-surgical procedure, the survey will be completed within 7 days prior to the initiation of radiation therapy. The survey may be completed during a regular clinic visit (if applicable) or sent and returned via mail. A review of the participant's medical record will be performed 3 months (Day 80 – 90) after their index BCS procedure. Treatments administered for the purposes of treating the primary breast cancer in the ipsilateral breast will be recorded in the eCRF. Treatments may include, but are not limited to, radiation therapy, chemotherapy, hormone, immunotherapy and surgery (e.g. re-excision, lumpectomy, mastectomy). If, at 3 months follow-up, the participant is no longer under the care of the *surgeon* who performed the index BCS procedure, the participant will be contacted via telephone to collect the follow-up data.

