- p. Any unresolved AEs present at Week 2 visit will be followed for an additional 7 days. Any unresolved SAEs will be followed for an additional 30 days. Patients with elevated liver enzymes will be followed until levels return to baseline.
- q. Medical chart reviewed to identify additional therapies related to the breast cancer diagnosis received since the Week 2 visit and within 1 year following Day 1 (e.g. additional surgeries, chemotherapy, radiation therapy, endocrine therapy, immunotherapy). In the event the patient is no longer under the care of the study investigator, the patient will be contacted via telephone.
- r. 3-month follow-up data must be collected 80-90 days post-procedure or within 7 days prior to commencement of radiation therapy, whichever occurs first.
- s. Includes assessment of neurological AEs (neurological AEs observed in the clinical trials of ALA HCl used for the visualization of glioma during surgical resection may be attributable to the greater amount of tissue resected in patients in the ALA arm as compared to control and are not expected to occur in breast cancer patients; nevertheless investigators must evaluate potential neurological AEs at each AE assessment time point)

SBI-CIP 20-002	Rev: v1.8	A prospective multi-center clinical study evaluating the use of PD G 506 A and the Eagle V1.2 Imaging System for the visualization of carcinoma during breast conserving surgery	Page: 65 of 157
-----------------------	--------------	--	-----------------

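### Table 12.2 defines a clinically significant liver elevation by closed grade 2 bands, so read literally a larger rise does not trigger follow-up to baseline; it should say grade 2 or higher

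*Combined protocol and SAP*

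**What the plan says.** Three places in the protocol govern liver follow-up after Week 2.

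- Section 12.7 sets the condition: "If liver enzymes are elevated from baseline (and deemed clinically significant according to the" table that follows it (Table 12.2). If it is met, the patient is followed until the values are back at baseline.
- Section 13.3 gives the same instruction and points to Section 12.7 for what counts as elevated.
- Footnote p of the Schedule of Activities (Section 12.1) says: "Patients with elevated liver enzymes will be followed until levels return to baseline". It names no threshold and does not mention Table 12.2.

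The column of Table 12.2 that serves as the test is headed "CTCAE v5.0 Grade 2 (moderate) as criterium to judge if elevation of liver enzymes should be deemed clinically significant". Its entries are ranges:

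- AST and ALT, normal baseline: "> 3.0 – 5.0x institutional* ULN if baseline normal"
- AST and ALT, abnormal baseline: "> 3.0 – 5.0x baseline if baseline abnormal"
- Bilirubin, normal baseline: "> 1.5 – 3.0x institutional* ULN if baseline normal"
- AP, normal baseline: "> 2.5 – 5.0x institutional* ULN if baseline normal"

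Neither the heading, the rows nor the note under the table adds that higher grades also count. A left-hand column gives other limits, such as "AST: > 2.5x institutional ULN", which match exclusion criterion 10 in Section 9.3.

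**The concern.** A rule for deciding which laboratory rises need follow-up should become no less demanding as the rise gets larger. A closed grade 2 band breaks that: it admits a moderate rise and drops a larger one. Because Section 13.3 borrows the Section 12.7 definition, the two sections that state the rule in the body of the protocol share the defect.

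Footnote p has no ceiling, so it disagrees with them for values above the band. It cannot be set aside as a loose summary, because the opening of Section 12 makes the schedule's requirements binding. At stake is whether patients with the largest rises are under a mandatory instruction to be followed back to baseline, and whether two sites would handle the same result in the same way.

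**Working it through.** There is no planned figure to reproduce. The check applies each text to example values.

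**Inputs.** Bands from Table 12.2, normal baseline: AST/ALT above 3.0 and up to 5.0 times ULN; bilirubin above 1.5 and up to 3.0 times ULN. Footnote p: no threshold. The Week 2 visit falls on Day 10–14.

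**Is follow-up to baseline required?**

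| Week 2 value (× ULN) | 12.7 as printed | 12.7 as grade 2 or higher | Footnote p, broad reading |
|---|---|---|---|
| AST/ALT 2.0 | No (2.0 < 3.0) | No | Yes |
| AST/ALT 4.0 | Yes (3.0 < 4.0 ≤ 5.0) | Yes | Yes |
| AST/ALT 6.0 | No (6.0 > 5.0) | Yes (6.0 > 3.0) | Yes |
| Bilirubin 1.2 | No (1.2 < 1.5) | No | Yes |
| Bilirubin 2.0 | Yes (1.5 < 2.0 ≤ 3.0) | Yes | Yes |
| Bilirubin 4.0 | No (4.0 > 3.0) | Yes (4.0 > 1.5) | Yes |

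The bilirubin entries under footnote p assume that bilirubin counts there as a liver enzyme, as it does in Table 12.2. The broad reading takes footnote p to cover every elevation. The footnote marker sits on the adverse-event row of the schedule, not on the blood-work row, so a narrower reading is also possible: only elevations recorded as adverse events. On that reading the last column holds only for such elevations, and the disagreement below the band shrinks or disappears.

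**Which rows matter in practice.** AP is not in the Week 2 panel (CBC, AST, ALT, total bilirubin, creatinine), so its row applies only if AP is measured to investigate an event. Criterion 10 excludes bilirubin above ULN at entry, so the abnormal-baseline branch should not arise for bilirubin. It can arise for AST and ALT, which may be up to 2.5 times ULN at entry.

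**What the general rules require instead.**

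- Non-serious adverse event (13.3): 7 more days. 10 + 7 = 17 and 14 + 7 = 21, so to about Day 17–21.
- Serious adverse event (13.3): at least 30 more days. 10 + 30 = 40 and 14 + 30 = 44, so to at least Day 40–44, and until resolution or stabilization.
- Any adverse event (13.4.1.1): until the treating surgeon considers it adequately resolved.
- Pausing rules (13.5): three grade 3 events probably or definitely related to the drug, or three so related to the device, pause the study, as does any serious event at least possibly related to either.

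None of these requires an individual patient's values to return to baseline.

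**The case against.** The strongest reply is that no competent site would treat AST at 6 times ULN as less significant than AST at 4 times. The note under Table 12.2 compares its wording with the CTCAE definition, which suggests that the ranges were copied from the grade 2 entry and that grade 2 was meant as the entry point. The amendment history in Appendix 7, useful here only as a sign of intent, describes the definition as based on a grade 2 event. Larger rises are also covered by footnote p, can be recorded as adverse events, and may reach the data safety monitoring board through the pausing rules.

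Most of this stands, and it limits the severity. It does not remove the defect: the printed criterion still gives the wrong answer when followed, and the fallback rules have different end points.

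A reader might infer that patients with marked liver injury would go unmonitored. The documents do not support that. Week 2 values are collected for everyone, and the rules above still apply. A reader might also infer a flat contradiction for every small rise. That depends on the broad reading of footnote p, which its place on the adverse-event row leaves open. The left-hand column of Table 12.2 adds little either way: its limits match criterion 10, and they do not remove the ceiling in the column that serves as the test.

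**Conclusion.** The point holds as a wording error in a safety threshold. Under Section 12.7 as printed, and Section 13.3 through it, AST or ALT above 5.0 times ULN, or bilirubin above 3.0 times ULN, with a normal baseline, does not trigger follow-up to baseline, while a smaller rise inside the band does. Footnote p disagrees with this above the band; below it the disagreement is conditional on how the footnote is read.

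The conclusion rests on a literal reading of the bands. The intended reading is almost certainly grade 2 as a minimum, which makes the correction uncontroversial. How many patients it would affect cannot be stated, since the protocol gives no frequency for such rises. Efficacy endpoints, sample size and type I error are untouched. The change should be made, but it is not critical.

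**What to change.** In Section 12.7 and Table 12.2, write CTCAE v5.0 grade 2 or higher, with no upper bound:

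- AST or ALT above 3.0 times ULN, or above 3.0 times baseline if baseline is abnormal;
- bilirubin above 1.5 times ULN;
- AP above 2.5 times ULN (or baseline, if abnormal), if it is measured.

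Section 13.3 then needs no change.

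As a secondary alignment, have footnote p refer to Section 12.7. On the broad reading this ends mandatory follow-up to baseline for rises below grade 2, such as AST at 2.0 times ULN, so the sponsor should first confirm that this is intended. If it is not, keep footnote p and bring Section 12.7 into line with it.

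The cost is a few more repeat liver tests than the literal Section 12.7 rule would require. The wording must also go through a protocol amendment, which under Section 18.1 needs sponsor and ethics board approval and, where required, notice to or approval by the regulator. No new procedure is added.
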